5.2 Specific Aims 1-3

Compare effectiveness of financial incentive, environmental strategy, and combined arm to control during Phases I and II. For expected weight change between months 0-18 of -8 kg, -5 kg and 0 kg in the combined, intervention and control groups, respectively (a net difference between single intervention and control groups of 5 kg and between combined intervention and control groups of 8 kg) and assuming a standard deviation (SD) of weight loss of 5 kg, 65 participants per group provide greater than 90% power to detect a difference with each intervention arm and control. With this sample size, there will also be approximately 87% power to detect a difference between the combined intervention arm and each of the single intervention arms. These calculations assume a 20% missing rate at the end of Phase II and hypothesis testing done using the Holm p-value correction for multiple comparisons (more details provided below).

5.3 Specific Aim 4

Compare effectiveness of financial incentives and environmental strategies and combined arm during Phases I and II.

6. Secondary Outcome Variable(s)

Specific Aim 5

6.1 Compare the cost differences between each arm relative to the effectiveness measured by incremental weight loss achieved.

7. Study Instruments

7.1 Surveys/Assessments will be administered during various time points throughout the study via the online Way to Health (WTH) study platform

7.2 Medical history variables will be obtained as part of eligibility screening on the WTH study website.

7.3 Demographic measures will be collected at baseline (race, income, household size, education).

7.4 Physical Activity: The Global Physical Activity Questionnaire (GPAQ) measures adherence to national recommendations for moderate (30 minutes moderate physical activity 5 days per week) and vigorous (20 minutes continuous vigorous activity on 3 days per week) physical activity recommendations. This will be collected at 0, 6, 12, 18, and 24 months.

7.5 Dietary Behavior: The Food Intake 3 Factor Eating Questionnaire will be collected at months 0, 6, 12, and 18, and 24.

7.6 Stages of Change Model [Transtheoretical Model (TTM)], a commonly used measure of behavioral change which envisions the process of behavior change as stages through which an individual may progress, regress, or cycle as needed. This correlates with many types of health behaviors within different populations. This will be measured at 0, 6, 12, 18, and 24 months.

7.7 As an ongoing measure of health-related quality of life we will use the SF-8 form (shortened version of SF-36, to assess quality of life in different domains in the general population) to reduce data collection and respondent burden. The SF-8 form will be administered at 0, 6, 12, 18, and 24 months.

7.8 We will use the EuroQol survey at 0, 6, 12, 18, and 24 months. The EuroQol survey is an assessment for overall quality of life.

7.9 Biometric assessment data, medical benefit claims information, and wellness program activities data:

Biometric assessment data will be obtained as part of their routine biometric assessments by the participant's employers (or 3rd party wellness vendors who provide wellness services for employees of IBC, the City of Philadelphia, and SEPTA), all of whom share the same insurance carrier, Independence Blue Cross. {height; weight; blood pressure; cholesterol; glucose; HbA1c (if applicable to participant)}. The opportunity to have these data collected for free are available to employees at SEPTA, IBC, and the City of Philadelphia as part of annual wellness biometric screening. Approximately 30% of all

employees participate in biometric screening. We will use this as a secondary measure for exploratory analyses.

Medical benefit claims information will be collected from the participants' insurer, Independence Blue Cross, which is relevant to our research.

Information on the participants' use of wellness program activities provided by the employers will be collected (the City of Philadelphia, IBC, SEPTA).

- The use of wellness program activities and biometric screening results will only be collected from the time participants enroll in the study until their completion date of the study. The medical benefit claims information will be collected starting from one year prior to participants' enrollment in the study, until their completion date of the study.
- The three categories of data listed above (biometric assessment data, medical benefit claims data, and wellness program activities) will be included in the informed consent form. In addition, all necessary Data Use Agreements, including the method of transfer to the University of Pennsylvania, will be executed and communicated to the IRB prior to the transfer of all data.

7.10 Withings Scale: Digital scales will be distributed to subjects in this study to measure and electronically deliver subjects' weight measurements throughout the study using a secure wireless connection.

8. Study Design

8.1 Research Design and Methods

Study participants will be obese employees recruited from three employers: SEPTA, IBC, and the City of Philadelphia. We will structure the first 6 months of the study (Phase I) as a weight loss phase in which participants will be encouraged as a weight loss goal to lose 0.5 pound per week [Note: weight loss targets for sample size calculations use kg to fit in with the literature but we will use pounds for the incentive targets, as that is what Americans are most familiar with]. Phase II (months 7-18) will consist of a period of weight loss maintenance in which participants will be able to choose a weight loss goal each month of either 0 or 0.5, pounds of weight loss per week. Phase III (months 19-24) will be a period of post-intervention follow-up concluding with an in-person weigh-in at month 24.

Participants will be randomized to either a control group (information provision and the standard wellness program at each employer along with measurement of weight at 0, 6, 12, 18, and 24 months), a lottery-based financial incentive, or a series of environmental strategies and counseling regarding food intake and physical activity, or a combination of the financial incentive and environmental strategies. Participants in the incentive arm will be eligible for daily winnings based on the weights that are transmitted using wireless scales which we will provide so that they receive daily feedback on their winnings to keep weight loss goals salient. However, we will only provide the full payments based on validation of weight measurement at 6 months intervals, taking advantage of the motivating power of loss aversion by highlighting to participants that they only receive their daily winnings if they continue to

maintain weight loss (or lose further weight) (an approach we have used with great success in previous studies).

All participants will receive \$50 after validation of weight measurements at months 0, 6, 12, and 24, and \$75 at the 18-month time point, regardless of what their weight is, an approach we have used in many studies to minimize the risk of differential rates of lost to follow-up in the intervention and control arms. The study is powered to test the effectiveness of each intervention arm relative to control as well as the relative effectiveness of the intervention arms. A cost-effectiveness analysis will be conducted to examine potential for wider dissemination and implementation. Measures and time points are shown in Table 1 (attached with the protocol application). We will leverage existing annual biometric assessments done by each of our employer partners at baseline, 12 months, and 24 months for information on glucose, cholesterol, and blood pressure. Dependent measures for primary aims: We will use change in weight as the primary outcome measure. This will match our primary outcome with the tracking that participants are doing on their own at home using wireless scales.

Measures of mechanisms for degree of weight change: Approaches to assessing measures related to daily weight tracking, dietary behavior, physical activity, and psychosocial constructs are as follows: Ongoing tracking of participation: For all participants we will use the Way to Health system to track participation in their respective arm: (1) daily weigh-ins and receipt of incentives (incentive and combined arm); (2) daily weigh-ins and use of environmental strategies at home or at work (environmental, incentive, combined arm); (3) study follow-up visits attended regardless of arm. The Way to Health system will track this using a substantial degree of automation. In the Environmental and Combined arms, use of recommended strategies will be tracked by logs as described above. If necessary, a stepped approach to greater promotion of the strategies will be used to ensure adequate uptake or dose of the environmental strategies

8.2 Measurement of cost-effectiveness

We will conduct a within-trial analysis that directly compares incremental costs and maintenance of weight loss using data measured in the trial. The principal analyses will compare over 18 months the incremental cost effectiveness ratios estimated from the incremental costs and effects between each of the individual arms and the control group as well as the combined intervention versus each individual arm. The analysis will be from the employer perspective, as the employer faces the decision as to whether to implement this program. Secondary analyses will evaluate the same incremental cost-effectiveness ratios but: 1) use data following 6 months of post-intervention follow-up (24 month visit); 2) use data at 12 months, a common follow-up interval in employee health programs; and 3) use the limited social perspective (because participant costs are crucial to understanding the full economic impact of interventions). Measurement of cost: For the employer perspective, measured costs will include: 1) incentive payments; 2) administrative costs of providing the interventions; and 3) medical expenditures. For the limited social perspective, measured costs will include 1) the costs included in the employer's perspective, 2) exercise costs, and 3) costs of nonstudy counseling services. This social perspective is limited in that we include incentive payments (which are transfers and typically omitted from the social perspective) and federal fee schedules to cost out medical services (as a proxy

for social opportunity cost). Service use already documented in the study: Many of the services that will be costed out are already being measured in the clinical case report forms detailing participant adherence to daily feedback, lottery winnings, attendance and participation, dietary behavior, and physical activity. Project personnel diaries: Project personnel will complete time-diaries quarterly detailing their time spent on administrative tasks in the past week including time administering all participant related aspects of the intervention and usual care (excluding time related to general project administration). These tasks will be itemized by type of activity. They will also record the number of participant contacts by type of activity. Using personnel wages, these diaries will be used to estimate unit costs of administrative contacts. Elements of cost: 1) Incentive payments. Incentive payments to participants will be computed directly from the amount of incentive paid in the trial. The costs will include the daily lottery payments and the direct payments. 2) Administrative costs of program: The administrative costs of the incentive and environmental strategies interventions will include those for maintaining account balances, mailing payments and conducting follow-up visits, and other costs such as the scales used to weigh the participants. We will include project personnel costs by measuring the average time required for project personnel to conduct specific intervention-associated administrative tasks as opposed to general project/ evaluation administration using personnel wages to convert this administrative time to costs.

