
4. Overall Objectives/Specific Aims

Primary

1. Assess the effectiveness of a daily lottery-based financial incentive, relative to the control group, on cumulative weight loss over an 18-month period. *H1: Mean weight loss from baseline to 18 months among participants randomized to the lottery incentive will be at least 5 kg greater than among control group participants.*

2. Assess the effectiveness of environmental strategies, relative to the control group, on cumulative weight loss over an 18-month period. *H2: Mean weight loss from baseline to 18 months among participants randomized to the environmental strategies group will be at least 5 kg greater than among control group participants.*
3. Assess the effectiveness of the combined incentives and environmental strategies arm, relative to the control group, on cumulative weight loss over an 18-month period. *H3: Mean weight loss from baseline to 18 months among participants randomized to the combined arm will be at least 8 kg greater than among control group participants.*
4. Assess the comparative effectiveness of a combination of lottery-based financial incentives and environmental strategies on cumulative weight loss over an 18-month period. *H4: Mean weight loss among participants randomized to the combined arm will be at least 3 kg greater than among participants in either of the individual arms.*

Secondary

5. Assess costs of each of the intervention arms from both the employer and social perspective and compare cost differences between each arm relative to effectiveness measured by incremental weight loss achieved. *H5: From an employer's perspective, each individual intervention will have favorable cost-effectiveness ratios relative to control; the combined arm will have a favorable cost-effectiveness ratio relative to individual arms.*

5. Primary Outcome Variable

5.1 Change in weight from baseline to 18 months.

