
data, we may fit hierarchical or mixed effects models with and without accounting for informative missing data.

For Specific Aim 5, we will consider appropriate methods for cost effective analysis such as the models proposed below. We will assess the costs of each of the intervention arms from both the employer and social perspective and compare the cost differences between each arm relative to the effectiveness measured by incremental weight loss achieved. The principal incremental cost-effectiveness ratios between intervention and control arms will be from the employer's perspective and we will compare costs during the intervention from baseline to 18 months per unit change in weight. Secondary analyses may also 1) evaluate this same ratio but use either 6 months post- intervention data (24 month visit) or 12 months of intervention data (12 month visit) and 2) evaluate these 2 ratios using a limited social perspective. Cost models will use a generalized linear model with a log link and gamma family. Missing data strategies will parallel those described above. We will assess sampling uncertainty for the comparison of costs and effects by calculating parametric 95% CIs for the cost per kg lost and acceptability curves. Standard errors and correlation of the difference in cost and effect will be derived using a bootstrap procedure.

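### The cost-effectiveness plan names no lottery-versus-environmental contrast and no dominance step, and Sections 8.2 and 11.1 describe the principal ratios differently.

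*Combined protocol and SAP*

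**What the plan says.** Section 8.2 takes the employer's perspective over 18 months and defines the principal ratios as those "between each of the individual arms and the control group as well as the combined intervention versus each individual arm". That makes four: lottery vs control, environmental vs control, combined vs lottery and combined vs environmental. Combined vs control is not listed.

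H5 in Section 4 matches this: "each individual intervention will have favorable cost-effectiveness ratios relative to control; the combined arm will have a favorable cost-effectiveness ratio relative to individual arms".

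Section 11.1, on Specific Aim 5, first says the plan will "compare the cost differences between each arm relative to the effectiveness measured by incremental weight loss achieved", without listing pairs. It then refers to "The principal incremental cost-effectiveness ratios between intervention and control arms" and does not repeat the combined-versus-single ratios. Section 11.3 likewise frames the effect as relative to control.

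For uncertainty, Section 11.1 plans "calculating parametric 95% CIs for the cost per kg lost and acceptability curves", with standard errors and the cost-effect correlation from a bootstrap. No section gives a dominance, extended-dominance or frontier rule, or a threshold for a favourable ratio. The five comparisons under Holm (Sections 11.1 and 11.2) do not include lottery vs environmental.

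**The concern.** An employer reading the result faces four alternatives: usual benefits, lottery, environmental strategies, or both together. For alternatives of which only one is bought, ratios against a shared comparator do not produce a ranking. An arm that another arm beats on cost, with equal or better weight loss, keeps whatever ratio it has against control, and nothing in that ratio reveals the problem. H5 could then be read as confirmed for an arm that a better option displaces.

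The second issue is the combined arm. Section 8.2 prices it as a step up from a single arm, while the Section 11.1 wording prices it against control. The first is a marginal price and the second an average price, and they can differ by a factor of about two. An analyst has no text saying which section governs.

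This matters because Section 8.2 names the employer as decision maker, and Section 10.8 says the findings will feed into benefit design.

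**Working it through.** **Inputs from the documents (Section 11.2).** Expected 18-month weight loss: 8 kg combined, 5 kg in each single arm, 0 kg control. SD 5 kg. 65 analysable per arm. Expected incremental cost of the lottery: $810 (incentives).

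**Assumptions not in the documents.** Environmental cost per person E, beyond what the arms share, is varied. Costs add, so combined = $810 + E.

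**Step 1: the plan's own figure.** The documents state no cost-effectiveness ratio for any pair of arms, so I checked the effect inputs through the stated 87% power for 3 kg, combined vs single. A two-sample t-test with 65 per arm, SD 5 and two-sided alpha 0.025 (the Holm level once the three control comparisons are rejected) gives 87.4%. The figure reproduces.

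**Step 2: single arms against control.** Ratio = cost difference / kg difference.
- Lottery: 810 / 5 = $162/kg, for any E.
- Environmental: E / 5.
- Lottery minus environmental: ($810 - E) for 5 - 5 = 0 kg.

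With equal effects, whichever single arm costs more is dominated. At E = $200 the lottery costs $610 more for no extra weight loss, yet still shows $162/kg. At E = $1,215 the environmental arm costs $405 more for no extra loss, yet shows 1,215 / 5 = $243/kg.

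The problem does not depend on a tie. If the lottery achieved 4 kg, the environmental arm 5 kg and E were $405 (all illustrative), the lottery would show 810 / 4 = $202.50/kg against control while costing $405 more for 1 kg less.

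**Step 3: the combined arm.**

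| E | vs control, (810 + E)/8 | vs lottery, E/3 | vs environmental, 810/3 | Step from the cheaper single arm |
|---|---|---|---|---|
| $200 | $126/kg | $67/kg | $270/kg | $270/kg |
| $400 | $151/kg | $133/kg | $270/kg | $270/kg |
| $1,215 | $253/kg | $405/kg | $270/kg | $405/kg |

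The last column is the price on the cost-effectiveness frontier under these assumptions. In every row it is one of the two combined-versus-single ratios that Section 8.2 plans. It goes unseen only if the control ratio replaces them, or if the ratio against the dominated single arm is the one quoted (for example $67 instead of $270 at E = $200).

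**Step 4: precision of the missing contrast.** The 95% CI half-width for lottery minus environmental weight change is 1.98 × 5 × √(2/65) = 1.74 kg. The matching interval for cost cannot be computed, because the documents give no cost SD.

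**The case against.** A reader might infer that the plan uses control as the comparator throughout and so hides the combined arm's marginal price. The documents do not support that: Section 8.2 and H5 both set the combined arm against each single arm. The Section 11.1 sentence mainly fixes perspective and time horizon, and need not be read as displacing Section 8.2. What stands is an inconsistency to reconcile.

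It can also be said that the plan does compare the two single arms. Aim 5 speaks of cost differences between each arm, and Section 5.3 says "Compare effectiveness of financial incentives and environmental strategies and combined arm during Phases I and II". Because both single arms share one control, the point differences in cost and weight follow by subtraction. That is correct, but the interval, the joint uncertainty and a decision rule are still unspecified.

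Section 8.2 describes the employer's decision as whether to implement the programme, and ratios against usual benefits are a legitimate answer to that. They should stay. They do not answer which of three programmes to implement.

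Finally, the dollar figures are fragile. The equal 5 kg effects are planning values and make the costlier single arm dominated by construction. Employer cost also includes administration and medical expenditure. Lottery payouts depend on meeting weight goals (Section 10.6), so a combined arm losing 8 kg might earn more than $810, which would move the $270/kg step upward. All of this limits the figures to illustration; the structural gap does not depend on them.

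**Conclusion.** The point holds as a gap and an inconsistency in a secondary aim. No lottery-versus-environmental contrast or dominance step is specified, so a dominated single arm could satisfy H5 against control, and no threshold defines favourable. Sections 8.2 and 11.1 also differ on the principal ratios. If Section 11.1 governed, the combined arm would be shown at about $126-$151/kg against a $270/kg marginal step, given E of $200-$400 and additive costs.

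It would go too far to say that the lottery is dominated, since the documents give no environmental cost, or that the plan understates the combined arm's price as it stands, since Section 8.2 already contains the relevant ratio. The primary comparisons and the Holm procedure are unaffected. Section 11.2 says the trial was not powered for cost-effectiveness, so any ranking of arms will be uncertain. The change is worth making because it is nearly free.

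**What to change.** 1. Reconcile Sections 8.2 and 11.1 so that the combined-versus-single ratios remain principal. If combined vs control is also wanted, list it as supporting output.
2. Keep the pre-specified pairwise ratios and add a four-arm incremental analysis: order the arms by mean employer cost, flag dominated and extendedly dominated arms, and report ratios along the frontier.
3. Draw one acceptability curve across all four arms, using the bootstrap already planned.
4. Report lottery-minus-environmental differences in cost and in weight with 95% CIs (about ±1.7 kg for weight), as estimation only and outside the Holm family.
5. State that no arm is dropped on point estimates alone, and that H5 is interpreted alongside the frontier.

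The cost is some SAP wording and a modest amount of extra analysis on an unpowered secondary aim. It requires no new data and no change to the sample size or the primary tests.

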Healthy eating environmental change strategies will be designed to guide participants in identifying environmental influences on excess food intake and making environmental modifications easier for them to implement in their worksites, in the area around worksites, and in their homes. At the worksite, the strategies will emphasize identifying healthy vending options, healthy snack access, social environment change, and establishing healthy catering policies for work-based events. In the neighborhood near the worksite, strategies will include tools to help workers find healthy choices easily at restaurants and periodic promotions (arranged with vendors) to encourage trying new healthful prepared foods. Home environment changes will be guided by the Home Food and Activity Environment Audit tool, originally developed for research conducted by [name] and colleagues at the Emory Prevention Research Center and recently adapted for an urban, low-income community intervention. Physical activity environment change strategies will also include strategies for worksites, near worksites, and in homes. At the worksites, strategies will include individually-delivered prompts to use stairs, standing desks, and walking breaks. In the area near worksites, strategies will include guidance on safe, convenient walking routes, link to benefits for incentives toward gym memberships, and safe bicycling paths. The Home Food and Activity Environment Audit will address physical activity environments in homes. Environmental strategies will be communicated to participants in the Environmental and Combined study arms twice weekly during the first 6 months, and weekly during months 7-18.

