They will be varied to maintain interest and offer a variety of approaches that participants can use. The Way to Health platform will be programmed to send links to web and mobile intervention information, and to prompt participants who wish to have hard copy/paper copies of intervention materials. One week after a strategy tool is distributed, a simple log will be provided for participants to indicate their liking for, and use of, the various strategies. All participants in each of the three intervention arms will also receive a free wireless scale (value \$110) as this will be used to both obtain weights and provide participants with feedback. We are not providing these scales to participants in the usual care arm because that would not be consistent with usual care. Usual care: Employees of IBC, SEPTA, and City of Philadelphia are all offered the same wellness program that consists of: (1) yearly biometric screenings

for which members receive incentives to participate; (2) reimbursements for fitness and weight management program participation (up to \$150 per year for documentation of 120 workouts and up to \$150 for documentation of participation in Weight Watchers); (3) Eat Right for Life educational program which includes onsite seminar and workshop materials; (4) six visits with a registered dietician as part of health benefit; (5) free use of WebMD tools - members biometric data is uploaded or self-reported and tools are available to the member to set goals and track progress.

Psychological research has identified social support as a factor that can help support weight loss. In an effort to strengthen the social support environment for participants in the environmental strategies and the combined incentives and environmental strategies arms, we will create a “secret” Facebook group where participants in these arms will be encouraged to provide support and seek support from one another. We will encourage wall posts of text, healthy recipes, pictures related to nutrition, physical activity and the environment. The research study team will periodically post helpful links or tips that participants can use to improve their nutrition and physical activity environment.

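### The employer-perspective cost list does not name the fitness reimbursement to which only two arms are steered, so cost per kg is biased if paid use differs by arm

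*Combined protocol and SAP*

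**What the plan says.** **Perspective and cost list.** Section 8.2 gives the principal perspective and its reason: "The analysis will be from the employer perspective, as the employer faces the decision as to whether to implement this program". The costs follow: "For the employer perspective, measured costs will include: 1) incentive payments; 2) administrative costs of providing the interventions; and 3) medical expenditures". The same section then describes the first two items. On incentives: "The costs will include the daily lottery payments and the direct payments". Administrative costs are those of running the interventions, such as "maintaining account balances, mailing payments and conducting follow-up visits, and other costs such as the scales used to weigh the participants", plus staff time. The third item is not described. For the limited social perspective, a secondary analysis, section 8.2 adds "2) exercise costs, and 3) costs of nonstudy counseling services".

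**The benefit.** The usual-care text in section 10.4 describes a wellness programme offered to employees of all three employers. It includes "reimbursements for fitness and weight management program participation": up to $150 per year against 120 documented workouts, and up to $150 for Weight Watchers, with no period stated for the second.

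**The steering.** Among the physical-activity strategies for the area near worksites, section 10.4 lists a "link to benefits for incentives toward gym memberships". The strategies are sent only to the Environmental and Combined arms, twice weekly for six months and then weekly to month 18. Section 8.1 allows stepped-up promotion if uptake of the strategies is too low.

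**The data.** Section 7.9 says that information on participants' "use of wellness program activities provided by the employers will be collected", from enrolment to study completion. No section turns that information into a cost.

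**The concern.** An incremental cost should include whatever the intervention changes for the payer. A background benefit drops out of the difference between arms only when paid use is the same in both. Here one component of the intervention points two of the four arms at a cash benefit, so unequal use is a plausible result of the intervention itself.

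The plan already treats exercise as worth costing, but only in the social perspective, which it justifies by the importance of participants' own costs. The reimbursed part is not a participant cost; it falls on whoever funds the wellness programme.

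At stake are the ratios behind hypothesis H5. Extra paid use in the steered arms would make them look cheaper than they are. Lower paid use would push the error the other way.

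**Working it through.** **1. The plan's own cost figure.** Section 10.6 gives a 1-in-5 chance of $10 and a 1-in-100 chance of $100: 0.2 × 10 + 0.01 × 100 = $3.00 per eligible day, as stated there. Then $3.00 × 540 days (18 × 30) × 0.5 = $810, the incremental incentive cost in section 11.2. The factor 0.5 is an assumption. Section 11.2 does not state it, but section 2.4 reports that about half of incentivised participants reached goal in the group's earlier daily-lottery study. With the planned 5 kg, $810 / 5 = $162 per kg.

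**2. The omitted amount.** Let c be the reimbursement per paid user over 18 months and d the difference in paid uptake between two arms. The omitted incremental cost is c × d, and the shift in the ratio is c × d / (kg difference). It is zero when d = 0.

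**3. Fitness reimbursement only.** c = $150 × 1.5 years = $225, assuming proration and full payment to each extra user. The documents give no uptake by arm, so d is an assumed range.

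| Extra paid uptake | Omitted per participant | Per kg at 5 kg | $162 per kg becomes | Share of $810 |
|---|---|---|---|---|
| 0 points | $0 | $0 | $162.00 | 0% |
| 10 points | $22.50 | $4.50 | $166.50 | 2.8% |
| 20 points | $45.00 | $9.00 | $171.00 | 5.6% |
| 30 points | $67.50 | $13.50 | $175.50 | 8.3% |

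**4. Comparisons affected.** The steering differs in three: Environmental versus control (planned 5 kg), Combined versus control (8 kg) and Combined versus lottery (3 kg). The same $22.50 to $67.50 gives $22.50/8 to $67.50/8 = $2.81 to $8.44 per kg for the second, and $22.50/3 to $67.50/3 = $7.50 to $22.50 per kg for the third. Steering does not differ in lottery versus control or Combined versus Environmental.

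**5. The Environmental arm.** The $810 is lottery money, so it is a fair yardstick for the Combined arm but not for this one. No incremental cost is stated for the Environmental arm. Its one priced item is the $110 scale (section 10.4), and $22.50/110 to $67.50/110 is 20% to 61%. Staff time and visits would enlarge the base, so these percentages overstate the effect on the full cost.

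**6. Upper scenario.** If Weight Watchers is also annual and its use moves equally: ($150 + $150) × 1.5 = $450; × 0.10 to 0.30 = $45 to $135; / 5 kg = $9 to $27 per kg.

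**The case against.** **Equal use cancels.** The benefit is open to everyone, and section 8.1 gives control participants information and the standard wellness programme. The gym link is one item in a long menu, and payment needs 120 documented workouts, so a link need not change payouts. All of this stands. A reader might infer that the principal ratio is wrong as planned; the documents do not support that, because they give no uptake by arm.

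**The payer is not named.** Section 10.4 uses health-plan language in places, and the insurer may fund the reimbursements. This stands as a point to settle. However, section 7.9 describes the wellness activities as provided by the employers, and the plan already charges medical expenditures to the employer although participants are insured through Independence Blue Cross, itself one of the three employers. Consistent treatment, or a stated reason for exclusion, is needed.

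**Medical expenditures might cover it.** The item is undefined, so the omission is by not being listed, not by explicit exclusion. Section 8.2 also says that many costed services, including participation and physical activity, are already being recorded. That general statement does not make reimbursement an employer cost. Section 12.4 says claims data will not be used for the cost-effectiveness analysis, so capture through that item cannot be assumed.

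**It is small and secondary.** Against the $430 per kg that section 11.2 calls detectable with 80% power, $4.50 to $13.50 is about 1% to 3% (4.50/430 to 13.50/430). Section 11.2 also says the study was not powered on cost-effectiveness. This stands and limits the priority.

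**Conclusion.** The point holds conditionally. The principal cost list does not name an employer-programme cost that the environmental strategies may shift in two arms. If paid use differs, three ratios are biased; if it does not, nothing changes. The size for the fitness benefit is $22.50 to $67.50 per participant, or $4.50 to $13.50 per kg at 5 kg. That rests on an assumed 10 to 30 points of extra uptake, full payment, proration over 18 months and the employer bearing the cost. It is modest beside $810, and proportionally larger for the Environmental arm.

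Two wider inferences are not supported. The $9 to $27 per kg that includes Weight Watchers is only an upper scenario, because no text steers participants to that benefit or gives it an annual period. The lottery-versus-control ratio is not touched by the steering, although weight goals could change benefit use there too. This is a cheap improvement to a secondary analysis; the primary weight analysis is unaffected.

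**What to change.** In section 8.2 and the Aim 5 text of section 11.1:

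- Add employer-borne wellness-programme reimbursements (fitness and weight-management programme) as an employer cost item, costed by arm from the section 7.9 data from enrolment to 18 months. Section 7.9 promises use, not dollars paid, so apply use × benefit amount if payments are not supplied.
- Say who bears the reimbursements and what medical expenditures contain, reconcile that item with section 12.4, and confirm that nothing is counted twice.
- In the limited social perspective, count the reimbursed part of exercise and programme costs once.
- Report use of the benefit by arm.

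Screening incentives need not be added on this argument, since nothing steers any arm toward screening. The cost is a few lines of text and a little more analysis, with no new data stream planned. The environmental ratios may become slightly less favourable.
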